**Regulatory**

[name]

Original version:	09/08/17	
Updated:	10/09/17 12/19/17 01/29/18 03/12/18 06/29/18 08/27/18 07/15/19 09/16/19	
	08/12/21	Change primary regulatory contact on title

page. Clarification that any subjects who do not have evaluable tumor tissue from both the pre-treatment biopsy and post-treatment surgery will be replaced. (Sections 5.3, 5.4, 5.6, 15) This change is meant to allow replacement of subjects who have an active viral infection while on study, which would impact treatment related analysis and the primary objective of the study.

## 4 LIST OF ABBREVIATIONS

AE; adverse event  
ANC; absolute neutrophil count  
APC; antigen present cells  
BCRP; Breast Cancer Research Program  
CBC; complete blood count  
CBER; Center for Biologics Evaluation and Research  
CEA; carcinoembryonic antigen  
CMP; complete metabolic panel  
CNS; central nervous system  
CPC; Cancer Protocol Committee  
CRF; case report form  
CTC; Common Toxicity Criteria  
DAMP; damage-associated molecular pattern  
DC; dendritic cell  
DCI; Duke Cancer Institute  
DoD; Department of Defense  
DUHS; Duke University Health System  
ECG; electrocardiogram  
eCTD; electronic common technical document  
eIF; eukaryotic initiation factor  
ELISA; enzyme-linked immunosorbent assay  
ER; estrogen receptor  
E:T; effector to target ratio  
FDA; Food and Drug Administration  
FFPE; Formalin-fixed, Paraffin-embedded  
H&E; hematoxylin and eosin  
HER2; human epidermal growth factor receptor  
HIV; human immunodeficiency virus  
HRPO; Human Research Protections Office  
HRV2; human rhinovirus type 2  
HSA; human serum albumin  
ICS; Investigational Chemotherapy Services  
IHC; immunohistochemistry  
IND; investigational new drug  
IRB; Institutional Review Board  
IRES; internal ribosomal entry site  
IT; information technology  
IV; intravenous  
MMG; mammogram  
MRI; magnetic resonance imaging  
MOI; multiplicity of Infection  
NCI; National Cancer Institute  
NHP; non-human primate  
OARC; Office of Audit, Risk, and Compliance  
OncPV; Oncolytic Poliovirus

OR; operating room  
PAMP; pathogen-associated molecular pattern  
PD-L1; programmed death ligand 1  
PET; positron emission tomography  
PFS; progression free survival  
PO; by mouth (latin term *per os*)  
PR; progesterone receptor  
PRTBTC; Preston Robert Tisch Brain Tumor Center  
PT; prothrombin time  
PTT; partial thromboplastin time  
PV1S; poliovirus serotype 1 (SABIN)  
PVSRIPo; Polio/Rhinovirus Recombinant  
RIO; Research Integrity Office  
RNA; ribonucleic acid  
SAE; serious adverse event  
SGOT; serum glutamic-oxaloacetic transaminase  
SOC; standard of care  
SOP; standard operating procedure  
TCID; tissue culture infectious dose  
TIL; tumor infiltrating lymphocytes  
TNBC; triple negative breast cancer  
ULN; upper limit of normal  
WHO; World Health Organization

## 5 PROTOCOL SYNOPSIS AND RESEARCH SUMMARY

### 5.1 Purpose

To examine oncolytic poliovirus (OncPV) bioactivity in tumor tissue after intratumoral administration of PVSRIPO (Polio/Rhinovirus Recombinant) in women with invasive breast cancer.

#### Objectives (Exploratory):

To investigate PVSRIPO-mediated inflammation and immunity in women with stage II-IV invasive breast cancer.

1. **Primary Exploratory Objective:** To describe the change in the amount of tumor infiltrating immune cells in tumor tissue pre- and post-injection of PVSRIPO by H&E (Hematoxylin and Eosin).
2. **Other Exploratory Objectives:**
  - a. To examine tumor tissue pre- and post-injection of PVSRIPO for inflammatory and immune signatures using arrays, CD155 expression by immunohistochemistry (IHC), immune cell infiltrate by IHC and tumor infiltrating immune cells using flow cytometry (post-injection only).
  - b. To examine blood for inflammatory and immune signature using arrays, immune cell composition (antigen presenting cells, B cells and T cells), T cell activation by flow cytometry and B cell activation by ELISA and peptide arrays. Blood will be collected on day -7 (range day -7 to -10, before polio vaccine booster), day 0 (before PVSRIPO injection), day 2 (range day 1 to 2 after PVSRIPO), day 14 (range day 10 to 20, after PVSRIPO before surgery) and in follow-up at months 1 ( $\pm$  10 days) and 6 ( $\pm$  1 month) post-PVSRIPO.

#### Hypothesis

Administration of oncolytic poliovirus, PVSRIPO, in the tumor causes inflammation, which stimulates innate and adaptive immune activation, in invasive breast cancer.

### 5.2 Background and Significance

Breast cancer is the most common cancer in women in the United States, with an estimated 246,660 new diagnoses in 2016, and is the second leading cause of cancer death in women, with an estimated 40,450 women in the United States dying from the disease in 2016 (1). Breast cancer is a heterogeneous disease comprising several molecular subtypes, based on receptor status, specifically the estrogen receptor (ER), progesterone receptor (PR), and human epidermal growth factor 2-neu (HER2) receptor. These receptors are both prognostic but also predictive of response to targeted therapy.

Triple Negative Breast Cancer or TNBC (negative for ER, PR, and HER2) represents 15-20% of all breast tumors and has the poorest prognosis, with an earlier age of diagnosis, higher rate of local recurrence and distant metastases, and an elevated 5-yr mortality rate compared to ER positive cancers (Breast Cancer Facts and Figures, 2015-2016, American Cancer Society). Therapies that stimulate durable systemic immunity and selectively eliminate malignant cells will be critical for extending survival and reducing risk of recurrence in women with breast cancer. In several phase I trials targeting the immune

checkpoint PD-1/PD-L1, cancer immunotherapy has been shown to demonstrate some promise in TNBC by showing objective response rates in the metastatic setting.

PVSRIPO is a recombinant polio:rhinovirus chimera, engineered to eliminate neuronal competence and is devoid of neuropathogenicity upon inoculation in primates and humans. PVSRIPO specifically targets and destroys tumor cells and initiates innate and adaptive immune events in the host. PVSRIPO has demonstrated promise in a phase I study at Duke University in patients with recurrent WHO Grade 4 malignant glioma and is currently being investigated in a Phase 2 trial in recurrent WHO Grade 4 malignant glioma. A single, intratumoral infusion of PVSRIPO has been shown to result in durable tumor regression in select patients with malignant glioma even in the presence of neutralizing antibodies and an innate antiviral response.

This is a pilot study designed to study PVSRIPO bioactivity in invasive breast cancer following intratumoral injection. The endpoints are exploratory and will guide design of a phase I/II study of PVSRIPO and combinations of PVSRIPO with immune checkpoint blockade (for example PD-1/PD-L1) in women with breast cancer. This pilot study is funded by a grant from the Department of Defense (DoD) entitled “Regional oncolytic poliovirus immunotherapy for breast cancer” (Principal Investigator, [name].).

Although we plan to target the TNBC population as the intended population for this novel therapeutic, for this feasibility study we will broaden the eligibility criteria to include all tumor subtypes, as there is no biologic rationale to support differing toxicities from different invasive breast cancer subtypes. After safety is confirmed in this feasibility study, we will focus our efforts on the intended TNBC population.

### **5.3 Design and Procedure**

This pilot study is designed to assess PVSRIPO-mediated intratumoral bioactivity, inflammation, and immune events in women with invasive breast cancer. Enrollment target will include six women with invasive breast cancer. Women with stage II-IV invasive breast cancer with at least 1 cm of residual tumor after chemotherapy and scheduled for standard of care surgery will be eligible.

Polio vaccine booster will be administered 1 week, or up to 10 days, prior to PVSRIPO injection. On day 0, after pretreatment biopsy is obtained,  $1 \times 10^8$  TCID50 (tissue culture infectious dose) of PVSRIPO will be injected into the tumor mass. On day 14 (range 10-20 days), women will undergo standard-of-care (SOC) surgical resection of PVSRIPO-treated tumor. Women will have follow-up at 1-2 days after PVSRIPO injection, 1 month ( $\pm$  10 days) and 6 months ( $\pm$  1 month) after PVSRIPO for adverse events, disease status, and whole blood draw for research purposes.

Women will undergo a pre-treatment core needle biopsy with collection of research cores of tumor tissue prior to intratumoral injection of PVSRIPO. Ten to twenty days after PVSRIPO injection, tumor tissue will be collected at the time of SOC surgical tumor resection. The surgically resected tissue will be collected and processed as fresh and formalin-fixed paraffin-embedded (FFPE) tissue. The tissue will be used to evaluate tumor

infiltrating lymphocytes (TILs), CD155 expression, and inflammatory and immune signature using arrays. Any subjects who do not have evaluable tumor tissue from both the pre-treatment biopsy and post-treatment surgery will be replaced.

Additionally, inflammatory and immune analysis will be conducted using blood obtained on day -7 (range day -7 to -10, before polio vaccine booster), day 0 (before PVSRIPO injection), day 2 to 5 (range day 1-2 after PVSRIPO), day 14 (range day 10 to 20 after PVSRIPO, which is before surgery) and in follow-up at months 1 ( $\pm$  10 days) and 6 ( $\pm$  1 month) after PVSRIPO. Blood will be analyzed for inflammatory and immune signature using arrays, immune cell composition (antigen presenting cells, B cells and T cells), T cell activation by flow cytometry and B cell activation by ELISA and peptide arrays. This pilot study will enable a phase I/II study of PVSRIPO and combinations of PVSRIPO with immune checkpoint blockade (for example PD-1/PD-L1) in women with advanced breast cancer.

#### **5.4 Selection of Subjects**

**Eligibility Criteria:** This pilot study will include women with stage II-IV invasive breast cancer scheduled to undergo surgical resection. Target enrollment is six women with invasive breast cancer over 24 months. Patients will be recruited among patients receiving their treatment for breast cancer at Duke Cancer Institute (DCI). Any subjects who do not have evaluable tumor tissue from both the pre-treatment biopsy and post-treatment surgery will be replaced.

##### Inclusion Criteria

- Age  $\geq$  18 years
- Confirmation of invasive breast cancer including any of the following:
  - Triple-negative breast cancer defined as receptor status being estrogen receptor expression  $\leq$  10%, progesterone receptor expression  $\leq$  10%, and HER2/Neu expression by IHC 0 or 1+, or 2+ with fluorescence *in situ* hybridization confirming no amplification of HER2 on a pretreatment tumor sample.
  - Hormone positive breast cancer defined as receptor status being estrogen receptor expression  $>$  10%, progesterone receptor expression  $>$  10% prior to initiation of chemotherapy.
  - HER2+ breast cancer defined as HER2/Neu expression by IHC 3+ or fluorescence *in situ* hybridization confirming amplification of HER2 on a pretreatment tumor sample prior to initiation of chemotherapy. HER2+ and hormone positive (ie triple positive) breast cancers are included in this study.
- Stage II-III invasive breast cancer with  $\geq$  1 cm of residual tumor based on MRI, mammogram, ultrasound, or breast clinical exam as SOC after completion of neoadjuvant chemotherapy, OR Stage IV BC with  $\geq$  1 cm locally recurrent disease (i.e. chest wall recurrence only)
- ECOG  $\leq$  1
- Positive serum anti-PV titer prior to biopsy
- Received a boost immunization with trivalent inactivated IPOL™ (Sanofi-Pasteur) at least 1 week prior to administration of the study agent
- Hemoglobin  $\geq$  9.0 g/dl, ANC  $\geq$  1,000 cells/ $\mu$ l, platelets  $\geq$  100,000 cells/ $\mu$ l

- Women must have had last dose of chemotherapy at least 2 weeks prior to treatment with PVSRIPO
- Women must have at least 2 weeks minimum (ideal 3-4 weeks) of a wash-out period after any steroid administration (IV, PO, or intraocular)
- Serum creatinine  $\leq$  2.0 mg/dl, serum SGOT and bilirubin  $\leq$  2 times ULN (upper limit of normal)
- Women must provide written informed consent prior to enrollment on study, prior to conduct of screening procedures and enrollment on study
- Women of childbearing potential will have a negative serum pregnancy test at screening
- Women of childbearing potential must be willing to avoid pregnancy utilizing approved forms of contraception for the course of the study through 120 days after PVSRIPO injection
- Surgical resection of the tumor is planned and patient is willing to undergo surgical resection of the cancer

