## 9 INVESTIGATIONAL PLAN

### 9.1 Study Design

This is a single institution pilot study designed to assess PVSRIPO-mediated intratumoral bioactivity, inflammation and immune cell infiltration in 6 patients with invasive breast cancer. To maximize immunological stimulation, we will wait at least 2 weeks (ideal 3-4 weeks) after the last dose of chemotherapy or steroids to administer the polio vaccine booster. PVSRIPO will be injected into the tumor mass at  $1 \times 10^8$  TCID50 7-10 days after polio vaccine booster is administered.

Biopsy material will be obtained from tumor tissue immediately prior to virus administration and resected tumor tissue will be obtained at 10-20 days (ideally 12-16) after PVSRIPO at the time of surgical resection. The PVSRIPO-treated tumor tissue will be transported to Surgical Pathology by the Brain Tumor BioRepository (BTBR) Team, as directed by [name], MD or per clinical protocol, for gross examination and research tissue procurement, thereby safe-guarding the diagnostic integrity of the specimen. Additional expertise in breast pathology will be provided by [name] [name], MD, PhD.

Tissue deemed appropriate for collection (i.e. wasteful excess and of no diagnostic value) will be collected by the Brain Tumor BioRepository (BTBR) Team, as directed by [name], PhD, and transported to her lab for correlative molecular and immune analyses. Our primary objective is to determine change in the amount of tumor infiltrating immune cells in tumor tissue pre- and post-injection of PVSRIPO by H&E. We will also evaluate inflammatory and immune signatures using inflammatory and innate/adaptive arrays, CD155 expression and immune cell infiltrate by IHC and tumor infiltrating immune cells by flow cytometry (post-injection only).

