### **12.1 Pre-treatment Period**

Women with stage II-IV invasive breast cancer with a residual tumor mass of at least 1 cm by imaging, after completion of neoadjuvant chemotherapy will be included in this study. A polio vaccine booster will be given 7 to 10 days before PVSRIPO injection. Thirty-five ml whole blood will be drawn for immunological profiling before polio vaccine booster.

 At the discretion of the physician, MMG or ultrasound may be done the day prior to surgery

 MMG or ultrasound only done at the 6 ( $\pm$  1) month follow-up visit.

 At 1 month follow-up visit only.

 This is a take-home kit and does not involve a clinic/hospital visit. Days refer to days after PVSRIPO.

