### **15 STATISTICAL METHODS AND DATA ANALYSIS**

Six women with breast cancer will participate in this pilot clinical study. The study is designed as an exploratory pilot study only to assess PVSRIPO bioactivity. Any subjects who do not have evaluable tumor tissue from both the pre-treatment biopsy and post-treatment surgery will be replaced.

Our primary objective is to describe the change in the amount of tumor infiltrating immune cells in tumor pre- and post-injection of PVSRIPO by H&E. Given the small sample size of this study, descriptive statistics will be used to summarize inflammatory and immune signatures in tumor and blood, tumor infiltrating immune cell analysis, changes in immune cell composition in blood and changes in T cell activation in blood. Some statistical comparisons may be conducted in an exploratory manner.

Tumor specimens collected pre and post injection of PVSRIPO will be examined for inflammatory and immune signature using arrays, tumor infiltrating cells by H&E and IHC, and CD155 expression by IHC. The level of the immune checkpoint PD-L1 expression in tumor tissue before and after PVSRIPO injection will also be examined. Mean changes in these outcomes will be computed, and a paired t-test or Wilcoxon signed-rank test may be conducted with appropriate adjustment for multiple comparison.

Changes over time in inflammatory and immune signature using arrays, immune cell composition (antigen presenting cells, B cells and T cells) and T cell activation by flow cytometry will be described. Changes over time in B cell activation using ELISA and peptide arrays will be described. Measurements will be obtained on day -7 (range day -7 to -10, before polio vaccine booster), day 0 (before PVSRIPO injection), day 2 (range day 1-2 after PVSRIPO), day 14 (range day 10 to 20, after PVSRIPO before surgery) and in follow-up at months 1 and 6 (after PVSRIPO).

Additional descriptive analyses besides those described here may be conducted using the samples collected.

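### The chemotherapy wash-out runs to PVSRIPO in Section 5.4 but to the polio booster in Section 9.1, and the Section 5.4 steroid wash-out names no end point

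*Combined protocol and SAP*

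**What the plan says.** The inclusion criteria in Section 5.4 hold two wash-out rules. For chemotherapy: "Women must have had last dose of chemotherapy at least 2 weeks prior to treatment with PVSRIPO". For steroids: "Women must have at least 2 weeks minimum (ideal 3-4 weeks) of a wash-out period after any steroid administration". The steroid rule lists routes of administration but does not say to which event the two weeks run.

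Section 9.1 states one rule for both drug classes and ties it to a different event: "we will wait at least 2 weeks (ideal 3-4 weeks) after the last dose of chemotherapy or steroids to administer the polio vaccine booster". Its stated reason is to obtain the greatest immune stimulation. PVSRIPO then follows the booster by 7-10 days, as Section 12.1 also says: "A polio vaccine booster will be given 7 to 10 days before PVSRIPO injection".

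Section 11.1 sets no criteria of its own and refers the reader to Section 5.4.

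The sampling points hang on these same events. Section 12.1 places the first profiling sample ahead of the booster: "Thirty-five ml whole blood will be drawn for immunological profiling before polio vaccine booster". Section 15 opens its blood series with that sample and follows it with one on day 0: "Measurements will be obtained on day -7 (range day -7 to -10, before polio vaccine booster), day 0 (before PVSRIPO injection". The tumor baseline for the primary exploratory objective is taken on day 0 (Section 9.1): "Biopsy material will be obtained from tumor tissue immediately prior to virus administration".

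**The concern.** The booster and PVSRIPO are different days, so a two-week wait counted to one is not the same rule as a two-week wait counted to the other. Nothing in the documents says which prevails. Elsewhere the exclusion criteria treat the two events as distinct anchors: prior investigational agents are counted back from the booster, live vaccines from PVSRIPO. The choice of anchor therefore cannot be dismissed as loose wording.

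Two things are at stake. One is eligibility: staff screening from Section 5.4 may enrol a woman whose schedule Section 9.1 does not allow. The other is interpretation. The blood analyses describe changes over time in immune cell composition, T cell activation and B cell activation, starting from the pre-booster sample, in six women without a control group. If that sample is drawn while immune cells are still recovering from chemotherapy or steroids, later changes could contain recovery as well as booster and PVSRIPO effects, and the design offers no way to separate them. Section 5.2 says the results will guide a phase I/II study.

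**Working it through.** The plan gives no figure of its own to reproduce. The check is day arithmetic.

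**Inputs**
- Minimum wash-out W = 14 days (Sections 5.4 and 9.1).
- Booster b = 7 to 10 days before PVSRIPO (Sections 5.3, 9.1 and 12.1).
- The first blood sample is drawn just before the booster. The day 0 blood and the biopsy are taken just before PVSRIPO.

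**Formulas**
- Section 5.4 anchor (PVSRIPO): chemotherapy to pre-booster blood ≥ W − b; chemotherapy to day 0 ≥ W.
- Section 9.1 anchor (booster): chemotherapy to pre-booster blood ≥ W; chemotherapy to day 0 ≥ W + b.

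**Minimum days after the last chemotherapy dose**

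| Booster day | 5.4: pre-booster blood | 5.4: day 0 blood, biopsy, PVSRIPO | 9.1: pre-booster blood | 9.1: day 0 blood, biopsy, PVSRIPO |
|---|---|---|---|---|
| −7 | 14 − 7 = 7 | 14 | 14 | 14 + 7 = 21 |
| −8 | 14 − 8 = 6 | 14 | 14 | 14 + 8 = 22 |
| −9 | 14 − 9 = 5 | 14 | 14 | 14 + 9 = 23 |
| −10 | 14 − 10 = 4 | 14 | 14 | 14 + 10 = 24 |

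At every sampling point the two texts differ by b, that is 7 to 10 days.

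**Can both rules be met?** Yes, in one direction. A woman who meets Section 9.1 reaches day 0 at least 21 days after chemotherapy and so also meets Section 5.4. The converse fails. With the last dose on day −14 and the booster on day −7, the interval to PVSRIPO is 14 days, which satisfies Section 5.4, but the interval to the booster is 7 days, which breaches Section 9.1.

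**Steroids.** Section 9.1 gives the same minimums as for chemotherapy: 14 days to the pre-booster blood and 21-24 days to day 0. Section 5.4 gives no computable minimum. If its two weeks were assumed to run to the booster, the figures would match Section 9.1. If they were assumed to run to PVSRIPO, they would be 4-7 and 14 days. Neither assumption is stated.

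**Dependencies.** The 4-day figure rests on the 10-day limit in Sections 5.3, 9.1 and 12.1; the booster criterion in Section 5.4 requires at least one week and sets no upper limit. Table 1 also marks an immune-analysis draw at screening (day −28 to −7), which could lie closer to chemotherapy, but Section 15 does not list that sample, so it is left out here.

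**The case against.** The strongest reply is that the two rules are compatible. Section 9.1 is part of the same protocol, and a site that follows it draws the pre-booster blood no sooner than 14 days after chemotherapy. That stands as a reading: the 4-7 day case arises only if Section 5.4 is applied alone. It does not remove the fault, because Section 11.1 points to Section 5.4 alone and no text tells the site to apply the stricter rule.

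The second reply is that for steroids there is no contradiction: Section 5.4 is silent on the end point and Section 9.1 supplies one. That also stands. A reader might infer that the steroid criterion runs to PVSRIPO as the chemotherapy criterion does, but the documents do not say so. The steroid fault is an omission in the list that decides eligibility.

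Third, there are partial safeguards. Concurrent chemotherapy and steroid therapy are excluded, hemoglobin, neutrophil and platelet minimums apply, and a blood count with differential is scheduled at screening, day −7 and day 0. None of these fixes an interval, and there is no lymphocyte criterion.

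Fourth, the documents give no time course, direction or size for immune recovery, and the reason Section 9.1 gives for waiting concerns stimulation rather than protection of baselines. Nothing shows that 21-24 days would be free of recovery effects. This stands: part of the difficulty is the ordinary limit of a single-arm pilot, and the bias can be stated only as possible.

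**Conclusion.** The concern holds as an internal inconsistency. For chemotherapy the two sections name different anchors, 7-10 days apart. For steroids Section 5.4 names none while Section 9.1 names the booster. On Section 5.4 alone, the pre-booster blood may fall 4-7 days after chemotherapy, against at least 14 under Section 9.1. Day 0 sampling and PVSRIPO may fall at 14 days, against 21-24. These figures rest on the two-week minimum and the 7-10 day booster window.

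Several stronger readings are tempting and are not supported:
- That the baseline for the primary H&E objective could fall 4-7 days after chemotherapy. It is a day 0 biopsy, at least 14 days after chemotherapy under either text, and a day 0 blood sample shares that minimum. Only the pre-booster blood is exposed to the shorter interval.
- That every endpoint is a within-patient change. Flow cytometry of tumor-infiltrating cells is done after injection only.
- That the 7-10 day discrepancy can be scaled against the 10-20 days between injection and surgery. The anchor moves the earliest permitted day 0; it does not alter the interval between biopsy and resection.
- That recovery alone would produce a rise. The documents do not quantify recovery, so this remains an assumption.

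The correction should be made: the rule governs who is enrolled and when the first sample of an uncontrolled immune series is drawn. With six women and a descriptive analysis, the consequence is weaker interpretation of the blood changes, not an invalid primary result.

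**What to change.** Sections 5.4 and 9.1 must be reconciled so that both state the same anchor event and the same minimum interval, for chemotherapy and for steroids. Which event and which interval to use is for the investigators to decide; this review does not propose one.

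In Section 15, add a listing that shows, for each woman, the actual days from her last chemotherapy dose and from her last steroid dose to the pre-booster blood and to the day 0 biopsy, placed beside her changes in blood and tumor measures. This also serves any woman already treated, whichever text was followed.

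The cost is amendment wording and one listing. The dates are needed to verify eligibility. Table 1 provides for medical history and concomitant medications but does not state that last-dose dates are recorded, so confirm that the case report form captures them. Depending on the anchor the investigators keep, some women might wait about a week longer (7-10 days at the minimum intervals).
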